13.	Taking the Work Forward	. 20
14.	Intellectual Property (IP)	. 20
15.	Costing Schedule	. 21
16.	Funding Arrangements	. 21
17.	References	21

1. Study Synopsis/Profile

Study title	Investigating the tolerability and feasibility of transcutaneous vagus nerve stimulation following aneurysmal subarachnoid haemorrhage				
Study short title	tVNS in aSAH				
Study design	Two-arm randomised controlled trial				
Study participants	Inclusion criteria:				
	 Age >18 Admitted to STH neurosurgery Confirmed aneurysmal SAH on vascular imaging Within 5 days of 'Securing' aneurysm (i.e., successfully coiled or surgically following rupture) 				
	Exclusion criteria:				
	 Current or prior use of a vagus nerve stimulation Symptomatic bradycardia or PPM insertion Complete heart block Implantation of any other electrical stimulator (e.g. DBS) 				
Planned sample size	30 participants (15 in each arm)				
Planned study period	36 months				
Planned recruitment period	24 months				
Study assessments	 Deliver TVNS using the parasym device for 45 minutes twice daily for 5 days following aSAH intervention (coiling or clipping) Pulse width 25ms, frequency device standard (25 Hz), at maximum tolerated intensity, or 				

	20MA for patients who cannot report the maximum tolerated intensity • Clinical follow-up on discharge and at 1 month				
Objectives	s Primary				
•	To establish the tolerability, and feasibility of tVNS in patients following aSAH, including;				
	 Monitor tolerability for tVNS Symptom severity scores of mild or moderate in less than 1/3 of participants able to report symptoms Assess study feasibility recruit >1 patient per month of recruitment >80% of recruited patients completing primary outcome measures 				
	Secondary				
	 Monitor safety criteria for tVNS No SAEs reported to tVNS Unexpected AEs in less than 1/3 of participants Explore clinical outcomes including: rates of clinical or radiological DCI inpatient mortality inpatient length of stay Rate of complications: seizures, hyponatraemia, rebleed, hydrocephalus Outcome measures using questionnaires on discharge and at 1-month Disability assessment: modified Rankin Score, Barthel Index Assess frequency and severity of headache: Likert scale Explore mechanisms of action: Inflammatory markers at baseline and 5 days Explore response to tVNS: 				
	 Near-infrared cerebral spectroscopy Heart rate variability Pupillary reactivity 				

2. Research Questions

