The aims of the study will be to conduct a pilot RCT to investigate whether tVNS is a tolerable and feasible treatment for acute aSAH. To understand this we will recruit participants who have recently undergone acute securing procedures follow acute aSAH (coiling or clipping of aneurysm) to a 5 day programme of intervention (active tVNS vs sham) and collect outcome data (primary and secondary as per outcomes section). We will evaluate whether pre-defined success criteria are achieved for tolerability and feasibility and explore signals of effect on clinical outcome measures and mechanistic measures. Non-invasive vagal nerve stimulation has not been

studied in the acute period following aSAH outside of the remit of reducing headache. This should offer critical insights as to whether this intervention has potential to take forward to a larger phase 2/3 clinical study.

5. Background

Delayed cerebral ischaemia (DCI) is a multifactorial sequela of aneurysmal subarachnoid haemorrhage (aSAH) which occurs in up to 30% of patients, usually within 14 days of ictus. Diagnosis is by means of clinical and radiological assessment of a new neurological deficit in the absence of other causes. Alongside rebleeding, DCI is the strongest predictor of in-hospital mortality after aSAH and has a significant impact on morbidity.

The pathophysiology of DCI is complex and poorly understood, but emerging evidence supports a multifactorial model which includes arterial vasospasm, inflammatory processes, localised coagulopathy, and failure of cerebral autoregulation – this represents a vasculopathic progress, rather than purely vasospasm. Current management strategies for DCI focus on overcoming vasospasm, primarily by inducing hypertension, although this fails to address other important factors in the disease pathophysiology such as the inflammatory process. Interventions that target a multiple pathophysiological pathways may offer greater clinical benefits.

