6.5 Sample Size

A sample size of at least 30 has been chosen based on the number or participants required for the purposes of a feasibility assessment.⁹ It is also a practically feasible number of participants to recruit based on annual admission numbers of patients to the RHH and the timeframe of the recruitment period.

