6.7 Outcome Measures

Primary Outcome Measures – success criteria:

- Monitor tolerability for tVNS
 - Symptom severity scores of mild or moderate in less than 1/3 of participants able to report symptoms (based on Likert Scale 1-5; 1 representing no issues; 5 representing severe symptoms)
- Assess study feasibility
 - recruit >1 patient per month of recruitment
 - >80% of recruited patients completing primary outcome measures at 4 weeks follow up

These outcome measures will be collected during the participants inpatient stay over the intervention period using a data collection proforma (appendix) and taken from recruitment records kept contemporaneously. Safety assessment of SAEs / AEs will be collected each intervention day by our research team.

Secondary Outcome Measures:

- Monitor safety criteria for tVNS
 - No SAEs reported to tVNS
 - Unexpected AEs in less than 1/3 of participants
- Explore clinical outcomes including:
 - rates of clinical or radiological DCI (%)
 - inpatient mortality (%)
 - inpatient length of stay (days)
 - rate of complications: seizures, hyponatraemia, rebleed, hydrocephalus (%)
- Outcome measures using questionnaires on discharge and at 1-month
 - Disability assessment: modified Rankin Score, Barthel Index
 - Assess frequency and severity of headache: Likert scale
- Explore mechanisms of action:
 - Inflammatory markers at baseline and 5 days
- o Explore response to tVNS:
 - Near-infrared cerebral spectroscopy
 - Heart rate variability
 - Pupillary reactivity

These will be measured during the inpatient hospital stay up until discharge (Figure 1).

- Outcome measures using questionnaires at on discharge and at 4 week follow-up
 - Disability assessment: modified Rankin Score, Barthel Index
 - Assess frequency and severity of headache: Likert scale (1-10 where 1 is non-existent and 10 is extremely severe)
- Explore mechanisms of action measured at baseline and at the end of intervention (5 days):
 - Inflammatory marker analysis at baseline and 5 days (IL-1B, IL-6, IL-10, TNFa)
 - Concurrent WCC, CRP and infection will be recorded at these time points as these may confound results
- o Explore response to tVNS:
 - Near-infrared cerebral spectroscopy

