6.9 Intervention

We are using tVNS settings that are widely used in other neurological conditions (epilepsy, migraine)¹⁴. These include:

- o Pulse width 25ms
- Frequency device default (20 or 25Hz)
- Intensity below pain threshold.
- Frequency 45 minutes twice daily. On the basis of similarity to other studies, practicalities on the ward and clinical scenario

We have chosen a duration of 5 days based on the usual clinical pathway of inpatient management at the Royal Hallamshire Hospital, and have chosen to deliver the treatment twice daily to optimise the dose. This is a pilot study with feasibility outcomes and as such we will be exploring the feasibility of this treatment regimen.

The Parasym Device will be applied to the left tragus (figure 1) as this is the most common site for tVNS delivery in neurological studies and is associated with few afferents to the heart.

The intervention is aimed at supplementing routine clinical care, and as such, the doses of tVNS can be interrupted for care activities (therapy sessions, examinations, assessments etc) and resume afterwards. The overall minute duration will aim to remain 45 minutes twice daily.

[figure not shown]

Figure 1. Anatomy of the ear and the tragus (a). Parasym attached to the tragus (b)

The active intervention will be compared to sham tVNS where the vagal nerve stimulator will be attached to the earlobe instead of the tragus, in keeping with evidence that this does not cause vagus nerve stimulation and is in line with sham methods used in other studies. We do not anticipate that patients will have the intervention long enough to become familiar with the common sensations associated with true tVNS intervention. At the end of the intervention period, participants will be asked if they thought they had received true of sham tVNS to understand the blinding ability of the sham.

We will use the FNIRS Lumo ecosystem (Gower labs) to assess cerebral blood flow in the frontal lobes. We will complete a protocol where 6 optodes are placed bilaterally over the frontal and prefrontal cortices. We will complete and record resting state signals of oxyhaemoglobin and deoxyhaemoglobin for 5 minutes while patients are layed in bed with their eyes closed (or wearing an eye patch). Following the 5-minute rest phase, vagal nerve stimulation or sham stimulation will start

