6.10 Study Protocol

Patients (or their representatives if they lack capacity) who are eligible for entry into the will be approached by the treating clinical teams with information about the study. Those who are interested will be given an information sheet and time to consider the study. Those keen to participate will sign a consent form (or assent form for those that lack capacity) and baseline outcome measures will be performed.

Enrolled participants will be issued with a study number and randomised 2:1 (SealedEnvelope Ltd) stratified according to age (<65 and ≥ 65 years). They will then receive either active tVNS stimulation (tragus) or sham (earlobe), twice daily for 45 minutes per session for 5 days. We do not anticipate discharges from hospital earlier than 5 days as this is not routine practice in the neurosurgical unit.

Primary outcome measures of tolerability and feasibility will be collected daily by researchers delivering the intervention, and secondary outcome measures will be collected at the end of intervention or on hospital discharge as detailed in figure 2.

Following discharge from hospital participants will return for follow up clinic assessment at 4 weeks where questionnaire measures of functional recovery and adverse event reporting will be undertaken. After this the participants involvement in the study will be complete.

Figure 2: Study Schedule for Outcome Measures

	Baseline visit	Visit 1	Visit 2	Visit 3	Visit 4	Visit 5 (EOT)	discharge	At 4 weeks
Eligibility screening	Х							
Informed consent	Х							
Randomisation	Х							
Socio- demographic data	X							
Clinical data collection	X						X	
Questionnaires: Disability - mRS, BI, headache likert scale	X						X	X
Reporting of side effects, adverse events and tolerability		X	X	X	X		X	X
Intervention reporting – settings delivered, duration of intervention		X	X	X	X			
Pupillometry + recording of prescribed eye drops	X					X		
Heart rate variability	X					X		
fNIRS	Х					X		
Monitor blood test results (secondary outcome measures), collection of data on WCC/CRP and infection status	Х	X	X	X	X		X	
Inflammatory marker analysis	X					Х		

EOT = End of treatment; BI = Barthel Index;

fNIRS = Functional near infra-red spectroscopy

7. Data Management

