7.2 Statistical Opinion

This is a pilot study which hopes to form the basis of further grant funding for a larger study. This is a provisional study to demonstrate tolerability and feasibility. Further statistical advice would be sought should further funding be granted for future study. Primary outcome data will be reported descriptively (proportions, %).

Continuous data will be compared using parametric or non-parametric analyses depending on whether data distribution is normal or not. Categorical data will be compared using Chi-square or one-way ANOVA. However, due to the small sample size, appropriate power to detect significant differences for these measures will not be reached. This is primarily an exploratory study and most data will be reported descriptively.

Between group differences in baseline characteristics will be compared using parametric (T-Tests) and non-parametric (Mann – Whitney U, Chi squared) tests, depending on normality of distribution.

A secondary outcome of this study is safety of TVNS in patients who have suffered a subarachnoid haemorrhage. Utilising the definition of SAE, if no SAE's are reported which are deemed related to tVNS by the research team, then we can be 95% confident that the true SAE rate lies between 0 and 12%.¹⁵

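### The SAE criterion and its 0 to 12% bound rest only on SAEs judged related to tVNS, yet Section 7.2 labels the result the true SAE rate, and no safety criterion compares all-cause SAEs between arms

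*Protocol*

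**What the plan says.** Protocol Section 6.7 lists two safety criteria among the secondary outcomes. The first is "No SAEs reported to tVNS"; the wording is garbled, and its meaning has to be taken from Section 7.2. The second is "Unexpected AEs in less than 1/3 of participants".

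Section 7.2 supposes that no SAEs occur that are "deemed related to tVNS by the research team, then we can be 95% confident that the true SAE rate lies between 0 and 12" (per cent). The count is therefore filtered by the team's judgement of relatedness, while the quantity said to be bounded carries no such qualifier.

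Section 6.7 separately lists DCI, inpatient mortality, seizures, rebleed, hyponatraemia and hydrocephalus as clinical outcomes, each as a percentage. Section 7.1 says the analyses compare the two groups and report complications and outcomes descriptively. Section 6.2 describes the trial as single blind.

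**The concern.** The numerator and the conclusion refer to different things. Counting only events attributed to the device and finding none says something about the rate of attributed events. It says nothing about how often participants on tVNS have serious events of any cause.

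The distinction matters in this population. The Background section says DCI is a complication "which occurs in up to 30% of patients, usually within 14 days of ictus". A single rebleed, seizure, death or episode of DCI on tVNS could reasonably be judged part of the haemorrhage, hence unrelated and also expected. An event so judged passes the first criterion (not related) and the second (not unexpected). Both criteria could then be met while serious events of any cause were more frequent on tVNS than on sham.

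A comparison with the randomised sham arm does not depend on case-by-case attribution, yet neither safety criterion uses it. The attribution is made by the research team in a single-blind trial. The results are meant to support a larger multicentre application (Section 13), and a bound labelled as the SAE rate could be carried into that planning as something it is not.

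**Working it through.** **Inputs**
- Total sample size: "A sample size of at least 30 has been chosen" (Section 6.5).
- Arm sizes: 15 and 15 in the Synopsis; in Section 6.10 participants are "randomised 2:1 (SealedEnvelope Ltd) stratified according to age", which implies 20 and 10 if 30 are recruited. The direction of the 2:1 ratio is not stated; 20 on tVNS is assumed where it is used below.
- Stated bound: 0 to 12% with zero related SAEs (Section 7.2).

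**Step 1: reproduce the stated figure.** The exact two-sided 95% upper limit for 0 events in n is 1 − 0.025^(1/n). With n = 30 it is 1 − 0.025^(1/30) = 0.1157, or 11.57%, which rounds to 12%. The arithmetic is right for 0/30.

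**Step 2: ask what it bounds.** The zero in 0/30 is the number of participants with an SAE judged related to tVNS. The limit therefore applies to the probability that a participant has an SAE *so judged*. The all-cause SAE rate is that probability plus the probability of having only SAEs judged unrelated. Nothing in the calculation limits the second part.

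**Step 3: see how the two criteria treat one event.** Take a rebleed on tVNS that the team judges to be due to the haemorrhage.

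| Where it could count | Does it count? |
|---|---|
| SAE criterion, 6.7 | No: not judged related |
| Unexpected-AE criterion, 6.7 | No, if regarded as an expected complication |
| Bound in 7.2 | No: not in the numerator |
| Clinical outcomes, 6.7 and 7.1 | Yes: listed and compared by group, but not a safety criterion |

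An unattributed, expected SAE that is not on the clinical-outcome list, a cardiac event for instance, would count in none of the four rows.

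**Step 4: what an all-cause comparison would look like.** The counts here are assumed, for illustration only. Suppose 12/20 participants on tVNS and 3/10 on sham have at least one SAE of any cause, none attributed. The risk difference is 0.60 − 0.30 = 0.30. The Wilson limits are 0.387 to 0.781 for 12/20 and 0.108 to 0.603 for 3/10. Newcombe's interval is then:
- lower: 0.30 − √[(0.60 − 0.387)² + (0.603 − 0.30)²] = −0.07
- upper: 0.30 + √[(0.781 − 0.60)² + (0.30 − 0.108)²] = 0.56

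The interval runs from −7 to 56 percentage points. In the same data the SAE criterion is met and Section 7.2 licenses a statement of 0 to 12%.

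**Separate matter.** The 12% needs 28 to 30 participants in the denominator, so it includes the sham arm, whose earlobe placement the protocol describes as "in keeping with evidence that this does not cause vagus nerve stimulation". On tVNS recipients alone the same formula gives 16.8% (n = 20) or 21.8% (n = 15). That is a question of denominator; the mislabelling would remain even with the right one.

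**The case against.** The strongest reply is that Section 7.2 is one conditional sentence: it starts from related SAEs, and its natural reading is the true rate of those same events. On that view the defect is a missing qualifier. The reply has force, but the qualifier is missing from the safety statement a reader would carry away, so it still needs correcting.

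A reader might go further and infer that an excess of deaths, rebleeds or DCI would inevitably be reported as safe. The protocol does not support that. Those events are listed in Section 6.7 without any attribution filter, and Section 7.1 compares the groups, so an excess in them could be seen in the report. The outcome also depends on how the team attributes events, and the protocol gives no attribution rules from which to predict it.

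A reader might also infer that the 12% contradicts the protocol's own DCI figure. That needs three things the document does not supply: an all-cause reading of the sentence, the 30% taken as the rate although it is given as a ceiling, and every DCI counted as an SAE. Section 7.2 refers to a definition of SAE, but none appears in the text available.

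It can further be said that an all-cause SAE table is ordinary SAP material, and that with 30 participants the comparison will usually be inconclusive. Both are fair. The absence of a table is not the point; the point is that the protocol itself fixes the safety criteria and states the bound, and both rest on attribution alone. A wide interval is an honest account of what 30 participants can show.

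**Conclusion.** The point holds as a mislabelled bound together with safety criteria that rest on attribution and expectedness and leave the randomised control unused. The 12% is arithmetically correct for 0/30 (11.57%) but applies only to SAEs judged related to tVNS; the all-cause SAE rate is left unbounded. Both safety criteria could be met despite an all-cause excess on tVNS. How likely that is cannot be worked out from the protocol, because it depends on attribution practice. The listed clinical outcomes are a partial safeguard: they could reveal an excess in the events they name, but they feed no safety criterion and miss other SAEs.

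This conclusion assumes that the garbled criterion in Section 6.7 means relatedness, as Section 7.2 indicates, and that some serious events would be judged unrelated and expected. It does not depend on the DCI rate or on which allocation ratio is correct. The change is worth making before results are reported, since the safety statement will inform a larger trial.

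**What to change.** - **Section 6.7, wording:** state the criterion as no SAEs *related to* tVNS.
- **Section 6.7, addition:** add to the safety criteria the number of participants with at least one SAE regardless of attribution, by arm, from randomisation to the 4-week visit, with risk difference and 95% CI.
- **Section 7.2:** name the bounded quantity as the rate of SAEs *judged related to tVNS*, and state that no overall safety conclusion will be drawn from the attributed count alone.

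The cost is a few words and one table. SAEs and AEs are already collected on each intervention day (Section 6.7), and adverse-event reporting is already scheduled at discharge and 4 weeks (Section 6.10, Figure 2), so no new type of assessment is needed. The drawback is a wide and less reassuring interval, of the order shown in the 12/20 against 3/10 illustration, which should be presented as an estimate and not as a test.

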Is transcutaneous nerve stimulation a tolerable and feasible intervention to potentially improve clinical outcomes in aneurysmal subarachnoid haemorrhage (aSAH)?

3. Abstract/Summary

Background

Subarachnoid haemorrhage (SAH) is a type of brain bleed, which can be complicated by issues including delayed cerebral ischaemia (DCI) which causes stroke like symptoms, such as weakness, in up to 30% of patients. Current treatments for DCI focus on improving blood supply but fail to address other important factors including reducing inflammation.

Stimulation of a nerve in the neck called the vagus nerve, which can be done through the skin (transcutaneous vagus nerve stimulation, tVNS) is known to relax blood vessels and reduce inflammation and is approved in other conditions such as epilepsy.^{3,4} In animals, vagus nerve stimulation improves survival after aSAH, and is being studied in humans to reduce headaches after aSAH.^{5,6}

There is a theoretical role of tVNS in improving outcome after aSAH. We aim to study whether tVNS is tolerated, and feasible in aSAH.

Methods

This is a single centre, pilot randomised controlled trial (RCT); the participants will receive either tVNS or 'sham' tVNS, twice daily for 45 minutes for 5 days. We will monitor tolerability (symptoms) and feasibility (recruitment rates) for recruited patients. Secondary outcomes will include rates of side effects, complications from SAH, outcomes on discharge and 4 week follow up, and exploration of mechanisms of action and response to tVNS including levels of serum inflammatory markers (IL-1B, IL-4, IL-6, IL-10 and TNFa), functional near infra-red spectroscopy (f-NIRS), heart rate variability (HRV) and pupillary light reactivity (PLR).

Results

Rates of complications, side effects and recruitment will be reported descriptively and we will undertake simple between-group statistical analyses on secondary outcome measures. If proven to be tolerated and feasible, this study will provide the basis for a future larger trial design.

4. Aims of the Study

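### The secondary criterion on unexpected AEs is meant to judge tVNS but names no arm; read literally it pools active and sham participants, and a low sham rate can then mask a high active rate

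*Protocol*

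**What the plan says.** Protocol section 6.7 opens its secondary outcomes with the item "Monitor safety criteria for tVNS". Beneath it stand two criteria: one on SAEs attributed to tVNS, and "Unexpected AEs in less than 1/3 of participants". The synopsis (section 1) repeats both. Neither place says which arm, or both, forms the denominator of the second.

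Four other statements bear on the reading:
- Section 3 uses the noun for everyone randomised: "the participants will receive either tVNS or 'sham' tVNS, twice daily for 45 minutes for 5 days".
- Section 6.9 justifies the earlobe sham as "in keeping with evidence that this does not cause vagus nerve stimulation".
- On allocation, the synopsis has "30 participants (15 in each arm" (1:1), while section 6.10 has "randomised 2:1 (SealedEnvelope Ltd) stratified according to age" and does not say which arm is the larger.
- Section 7.2 says of a finding of no related SAE: "then we can be 95% confident that the true SAE rate lies between 0 and 12" per cent.

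**The concern.** A criterion that is to judge the safety of an intervention should be evaluated in the people exposed to it. On the protocol's own account, sham participants receive no vagal stimulation. If they are counted in the denominator, the rate held against one third is a weighted average of the two arms. Whenever the sham rate is the lower, that average understates the active rate.

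The threshold could then be met although well over a third of tVNS participants had an unexpected AE. Its meaning would also shift with the allocation ratio, on which the protocol contradicts itself. At stake is how the safety result is read when a larger trial is considered.

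**Working it through.** **1. Which denominator does the protocol's own safety arithmetic use?** Section 7.2 gives an upper limit of 12% for zero related SAEs. The exact two-sided 95% upper limit for 0 events in n is 1 − 0.025^(1/n):
- n = 30: 11.6%, which rounds to 12%
- n = 20: 16.8%
- n = 15: 21.8%

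The one-sided form, 1 − 0.05^(1/n), gives 9.5%, 13.9% and 18.1% in the same order, and the rule of three (3/n) gives 10%, 15% and 20%. Among the design denominators, only n = 30 (both arms together, two-sided) yields 12%.

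**2. When is the pooled criterion met?** It requires x/30 < 1/3. Since 10/30 equals 1/3, the largest count that meets it is 9. With s sham participants affected, up to 9 − s active participants may be affected:

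| Sham affected | Active, 15:15 | Active, 20:10 (assumed active:sham) |
|---|---|---|
| 0 | 9/15 = 60% | 9/20 = 45% |
| 1 | 8/15 = 53% | 8/20 = 40% |
| 2 | 7/15 = 47% | 7/20 = 35% |
| 3 | 6/15 = 40% | 6/20 = 30% |
| 4 | 5/15 = 33.3% | 5/20 = 25% |

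Once 4 of 15 or 3 of 10 sham participants are affected, the pooled criterion can no longer be met with more than a third of the active arm affected.

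**3. How often would it be met?** The protocol states no expected rate for either arm, so the rates here are assumptions: 50% in the active arm, and 0 to 40% in the sham arm. With A ~ Bin(n_A, 0.5) and S ~ Bin(n_S, p_S) independent, the pooled criterion is met with probability P(A + S ≤ 9):

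| Sham rate | 15:15 | 20:10 (assumed active:sham) |
|---|---|---|
| 0% | 85% | 41% |
| 10% | 59% | 27% |
| 20% | 35% | 17% |
| 30% | 17% | 9% |
| 40% | 7% | 5% |

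**4. Comparison with an active-arm criterion.** The same threshold applied to the active arm is met at 4/15 or fewer (26.7%), or 6/20 or fewer (30%). At a true active rate of 50%, P(A ≤ 4 of 15) = 5.9% and P(A ≤ 6 of 20) = 5.8%. This barely depends on which of the two allocations applies, whereas the pooled figure depends on it heavily. At a sham rate of 40% the two criteria behave about alike.

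**The case against.** **Pooling is inferred.** No sentence says that both arms are combined. The criterion stands under a tVNS heading, beside one on SAEs attributed to tVNS, so an active-arm reading is available. The n = 30 basis belongs to a different criterion and is circumstantial here. Section 7.1 says that the groups will be compared. This lowers confidence but does not remove the point. The literal noun covers both arms, the companion figure agrees with that, and the general statement in 7.1 sets no denominator. If the active arm was intended, the same edit is needed.

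**The sham rate may not be low.** Sham participants also have a device attached and have the same acute illness with the same complications. Nothing in the documents supports a large difference between arms, and the case with no affected sham participant is an outer bound. This stands, which is why a range is shown rather than a single scenario.

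**A reader might infer that the rule could declare tVNS safe when it is not.** The documents do not support that. Section 6.7 keeps the label of success criteria for the primary outcomes, and section 4 ties the pre-defined success criteria to tolerability and feasibility. No go/no-go decision or declaration of safety is attached to this threshold. It is one of two safety criteria, and section 7.2 describes the study as mainly exploratory and descriptive. An imbalance such as 9/15 against 0/15 would be expected to show in results by group.

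**The denominator could be left to a SAP.** In general it could. Here the protocol already states a threshold and a denominator, and the denominator does not match the stated purpose.

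**Conclusion.** The point holds as a defect of wording with a real but conditional effect. Read literally, and in line with the n = 30 basis of the 12% SAE limit, the criterion counts active and sham participants together. It can be met with up to 60% of 15, or 45% of 20, active participants affected.

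How likely that is rests on three things that the protocol does not settle: the AE rates (assumed), the allocation (15:15 or 2:1), and the direction of 2:1 (taken as active to sham). At an assumed active rate of 50%, pooling makes the criterion much easier to meet when the sham rate is 0 to 20%. The advantage has largely gone by 40%.

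The criterion is secondary and exploratory, and no decision hangs on it. Severity is minor to moderate, with medium confidence that pooling is what the text means.

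**What to change.** In the synopsis and in section 6.7, state the criterion as unexpected AEs in fewer than one third of the participants who received active tVNS, and report the sham rate alongside as the comparator. Reconcile the synopsis with section 6.10 on the allocation ratio and, if 2:1 stands, say which arm is the larger.

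If the SAE limit in section 7.2 is also meant for people exposed to tVNS, rebase it on the active arm: 21.8% for n = 15, or 16.8% for n = 20.

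The edit is one phrase in two places plus the allocation correction. The price is a smaller denominator, 15 or 20 instead of 30, and so a less precise rate. At a true active rate of exactly one third, the active-arm criterion is met only 40% (n = 15) or 48% (n = 20) of the time, so the result should be read as a descriptive signal.

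### DCI, complications and death are ascertained as outcomes only to discharge, a window that differs by patient and may differ by arm, and section 6.3 conflicts with this

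*Protocol*

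**What the plan says.** Section 6.7 of the protocol lists, as secondary clinical outcomes, "rates of clinical or radiological DCI", "inpatient mortality", inpatient length of stay, and "rate of complications: seizures, hyponatraemia, rebleed, hydrocephalus". All but length of stay are percentages, and none has a fixed number of days attached. The list closes with "These will be measured during the inpatient hospital stay up until discharge".

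Section 6.10 is consistent with that: it places secondary outcome collection at the end of treatment or at discharge. Figure 2 marks the clinical data collection row at baseline and discharge only. The same section provides a clinic visit after discharge, "at 4 weeks where questionnaire measures of functional recovery and adverse event reporting will be undertaken", and Figure 2 marks the adverse event row at discharge and at 4 weeks.

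Section 6.3 says something different: that all outcome measures are gathered at recruitment, at discharge and one month after discharge.

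On timing of risk, section 5 describes DCI as a complication "which occurs in up to 30% of patients, usually within 14 days of ictus". Section 6.10 does not expect discharge before 5 days and says nothing about later days.

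**The concern.** A percentage compared between two arms needs the same period of observation for everyone. Here the period ends at discharge, an event that follows randomisation, varies between patients and may itself respond to treatment. Length of stay sits in the same outcome list for that reason. If one arm goes home sooner, fewer of its events fall inside the window, and its DCI and complication rates look lower even when the underlying risk is the same.

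The stake is modest but real. Section 4 intends to explore signals of effect on clinical outcomes, and section 13 describes a follow-on trial of whether tVNS reduces complications after SAH. The pilot's rates and outcome definitions would feed that design. An analysis plan can set denominators or censoring rules, but it cannot recover post-discharge events that were never collected as outcomes. The collection schedule is fixed in this protocol.

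**Working it through.** The protocol gives no event count, power or sample-size figure for these outcomes, so there is nothing to reproduce. The check has two parts.

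**1. The sections side by side**

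| Place | When DCI, complications and death are ascertained |
|---|---|
| 6.3 | recruitment, discharge, and one month after discharge (all outcomes) |
| 6.7 | inpatient stay, to discharge |
| 6.10 text | end of treatment or discharge |
| Figure 2, clinical data collection | baseline and discharge |
| Figure 2, adverse events | visits 1 to 4, discharge, 4 weeks |

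Three entries agree on discharge and 6.3 does not. The closing sentence in 6.7 is also loosely placed: the list it follows includes questionnaires due at 1 month, which cannot be completed by discharge.

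**2. How much the window could matter (illustration only)**

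Inputs from the protocol: DCI up to 30%, usually by day 14 from ictus (section 5); 30 participants (section 6.5); 15 per arm (synopsis; section 6.10 gives a 2:1 ratio instead, but 15 serves for scale).

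Assumptions not in the protocol: true rate 30% in both arms, all onsets by day 14, onset uniform from day 3 (varied from day 0 to day 4), discharge day D counted from ictus and unrelated to DCI.

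Recorded rate = 30% × (D − 3)/(14 − 3). Expected events in 30 patients = 0.30 × 30 = 9.

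| All patients leave on day | Share of window seen | Recorded rate | Events missed of 9 |
|---|---|---|---|
| 8 | 5/11 = 0.455 | 13.6% | 4.9 |
| 10 | 7/11 = 0.636 | 19.1% | 3.3 |
| 12 | 9/11 = 0.818 | 24.5% | 1.6 |
| 14 | 11/11 = 1 | 30.0% | 0 |

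- Sensitivity to the onset assumption at D = 10: start at day 0 gives 30% × 10/14 = 21.4%; start at day 4 gives 30% × 6/10 = 18.0%.
- If only a quarter of patients leave on day 10 and the rest stay to day 14 or later: 30% × (0.75 + 0.25 × 0.636) = 27.3%, with 9 × 0.25 × 0.364 = 0.8 of an event missed.
- False difference between arms of equal risk, one wholly discharged on day 10 and the other on day 14 or later: 30.0 − 19.1 = 10.9 points, or 0.109 × 15 = 1.6 patients in an arm of 15. If only a quarter of the first arm leaves on day 10: 30.0 − 27.3 = 2.7 points, or 0.4 of a patient.

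With any window that covers day 14 for everyone, the assumed 30% is recovered whatever the discharge day.

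**The case against.** The case on the other side is substantial.

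- **Post-discharge time is not unobserved.** A reader might infer that nobody looks at patients after they leave. The documents do not support that: adverse events are reported at the 4-week visit, so a late seizure or rebleed could be recorded there. What remains is that such an event is not assigned to the named DCI, complication or mortality outcome.
- **No scoring rule is stated.** A reader might infer that early leavers are counted as event-free. The protocol gives no denominator or censoring rule for these percentages, and an analysis plan may supply one. It is fair to say only that nothing in the protocol prevents such counting.
- **Section 6.3 points the other way.** It is therefore not settled that collection stops at discharge. This turns part of the point into a contradiction, which itself needs resolving.
- **The highest-risk period may fall in hospital.** Section 6.1 says the five-day course covers it. That weakens the uniform-onset assumption and suggests that the loss is smaller than the larger figures above. It does not close the gap, because section 5 gives a period of up to 14 days and the highest-risk part is not the whole.
- **Discharge is probably not independent of DCI.** Patients who are deteriorating are unlikely to be sent home, which again makes the illustration an upper-end picture.
- **Inpatient mortality is a legitimate, explicit outcome.** That stands. It is not an error as defined, but it cannot also serve as a death rate over a common period.
- **The outcomes are exploratory.** Section 7.1 reports them descriptively and section 7.2 concedes that power is inadequate. That stands and limits the severity.

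**Conclusion.** The point holds in a limited form. Sections 6.7 and 6.10 and Figure 2 tie DCI, the four complications and death to a patient-specific window whose length is itself compared between arms, and section 6.3 contradicts them. Events after discharge may surface as adverse events but are not captured as the named outcomes, so between-arm percentages can differ because of length of stay alone.

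The size cannot be established, because the protocol gives no distribution of discharge days. Under the assumptions shown, it runs from less than one missed event among 30 patients (a quarter discharged on day 10) to about three (all discharged on day 10), with nothing missed if everyone stays to day 14. The effect is probably towards the small end. No tolerability, recruitment or completion criterion depends on these outcomes. This is a worthwhile, inexpensive improvement and not a flaw that undermines the pilot.

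**What to change.** 1. Reconcile the synopsis, sections 6.3, 6.7 and 6.10, and Figure 2, so that each outcome has one stated time of ascertainment.
2. Define DCI, each complication and all-cause death over one fixed window from randomisation, the same for everyone. Day 28 is an example. It covers the 14-day DCI period, since randomisation follows ictus.
3. Record the date of every such event. The 4-week visit is timed from discharge, so an extra tick in Figure 2 does not by itself create a common window; events must be dated and cut at the fixed day. A visit 4 weeks after discharge falls at or after day 28 from randomisation, so the information will be available for those who attend.
4. Add clinical data collection to the 4-week column of Figure 2, completed from the visit and from the hospital record, which also covers deaths and non-attenders.
5. Keep inpatient mortality and inpatient length of stay as descriptive outcomes.

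The cost is protocol wording, dated fields at a contact that already takes place, and a short record check. The downside is that some post-discharge events will be reported and not directly observed. Hyponatraemia and radiological DCI after discharge would be found only where tests were done for clinical reasons, which should be stated when the rates are reported.
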